10.8 Resistance Analyses

For all subjects, full length NS3/4A or NS5A from baseline samples will be sequenced by next generation sequencing (NGS). For subjects who experience virologic failure (ontreatment virologic failure or post-treatment relapse as defined in Section 10.1), full length NS3/4A and NS5A genes from the first sample after virologic failure with HCV RNA \geq 1000 IU/mL will be sequenced by NGS. An appropriate subtype specific prototypic reference sequence will be used for comparison with sequences from samples. Subjects who experience virologic failure will be referred to as subjects in the primary virologic failure (PVF) population, and a listing by subject that includes HCV subtype, IL28B genotype, reason for SVR₁₂ non-response, time point(s) sequenced as closest to time of VF, and HCV RNA value at the VF time point(s) will be produced for these subjects. In addition, all listings described below will display HCV subtype and reason for SVR₁₂ non-response in the subject identifier for each subject. A separate listing will delineate all subjects in the PVF population for whom no sequencing was performed (e.g., lost to follow-up while HCV RNA \leq 1000 IU/mL).

Subjects treated with study drug who do not achieve SVR_{12} due to reasons other than virologic failure (prematurely discontinued study drug with no on-treatment virologic failure, HCV reinfection, missing SVR_{12} data or other reasons as described in Section 10.1, Reasons for SVR_{12} Non-Response), but have a time point with HCV RNA ≥ 1000 IU/mL after treatment discontinuation, will have the sample at that time point sequenced. These subjects will be referred to as the non-PVF population. A listing of all subjects in the non-PVF population with post-baseline sequencing available will be created that is similar to the listing of subjects in the PVF population with post-baseline sequencing available.

For each DAA target, resistance-associated signature amino acid positions and a key subset of amino acid are listed in Table 6. Appropriate subtype specific prototypic reference sequence will be used for comparison with sequences from samples.

Genotype	Signature Amino Acid Positions	Key Subset of Amino Acid Positions
NS3/4A		
1a	36, 43, 54, 55, 56, 80, 107, 122, 132, 155, 156, 158, 168, and 170	155, 156, 168
1b	36, 54, 55, 56, 80, 107, 122, 155, 156, 158, 168, 170, and 175	155, 156, 168
2, 3, 4, 5, 6	36, 43, 54, 55, 56, 80, 155, 156, 166 (GT3 only) and 168	155, 156, 168
NS5A		
1a	24, 28, 29, 30, 31, 32, 58, 62, 92, and 93	24, 28, 30, 31, 58, 92, 93
1b	24, 28, 29, 30, 31, 32, 54, 58, 62, 92, and 93	24, 28, 30, 31, 58, 92, 93
2, 3, 4, 5, 6	24, 28, 29, 30, 31, 32, 58, 92, and 93	24, 28, 30, 31, 58, 92, 93

Table 6.List of Genotype-Specific Signature Amino Acid Positions and a
Key Subset of Amino Acid Positions

Included time points for analyses on samples from subjects who do not achieve SVR_{12} are 1) the sample closest in time after failure/discontinuation with an HCV RNA level of $\geq 1000 \text{ IU/mL}$, and 2) 24 weeks post-DAA treatment, provided that resistance-associated variants were detected at the time of failure/discontinuation

The following definitions will be used in the resistance analyses:

- Baseline variant: a variant by NGS in a baseline sample (≥ 2% or ≥ 15% prevalence within a subject's viral population depending on variant frequency threshold utilized) that was not present in the appropriate prototypic reference amino acid sequence for a given DAA target (NS3/4A or NS5A)
- Variant at signature amino acid position: variant (relative to reference) present by NGS at a detection threshold of $\ge 2\%$ or $\ge 15\%$ (depending on variant

frequency threshold utilized) within a subject's viral population in a baseline or a post-baseline sample at a signature amino acid position

- Post-baseline variant: an amino acid variant in a post-baseline time point sample that was not detected at baseline (< 2%) in the subject and is detectable in ≥ 2% of the sequences from the post-baseline sample
- Enriched variant: variant present in both the baseline and a post-baseline sample whose prevalence in the post-baseline sample is at least 20 percentage points greater than the prevalence in the baseline sample [(post-baseline % baseline %) ≥ 20]
- Treatment-emergent variant by NGS: A post-baseline variant or an enriched variant

Analysis will be Performed Separately for each HCV Subtype Within each Listing.

Analysis 1: The following analyses will be performed for all subjects:

- A listing of all baseline variants (≥ 2% detection threshold) at signature resistance-associated amino acid positions for each DAA target (NS3/4A and NS5A) (ITT).
- A listing of all baseline variants (≥ 15% detection threshold) at non-signature resistance-associated amino acid positions for each DAA target (NS3/4A and NS5A) for subjects in PVF population.
- A listing of baseline variants (≥ 15% detection threshold) at signature amino acid positions in subjects with variants across both NS3 and NS5A, or those with multiple baseline variants within any one target (NS3 or NS5A) (ITT population).
- The number and percentage of subjects with baseline variants at detection-thresholds of ≥ 2% and ≥ 15% for variants at signature amino acid positions (ITT). This table includes prevalence of each baseline variant, and a summary of number of subjects with variants in NS3 only, NS5A only, and NS3 + NS5A. Include the number of GT2 6 subjects with variants in NS3 only, NS5A only, any in NS3, any in NS5A, any in NS3 or NS5A, any in NS3 + NS5A.

- Total number and percentage of subjects with baseline polymorphisms *at a key subset of amino acid positions* in NS3 only, in NS5A only, any in NS3, any in NS5A, any in NS5A, any in NS3 + NS5A (ITT), by subtype, and total.
- Total number and percentage of subjects with baseline polymorphisms *at a key subset of amino acid positions* in NS3 only, in NS5A only, any in NS3, any in NS5A, any in NS5A (ITT), by genotype, and total.

Analysis 2: The impact of baseline variants on treatment outcome will be assessed for **mITT-GT-VF** population as follows: for each variant, the SVR₁₂ rate will be calculated for subjects with and without the variant and the 2 rates will be compared using Fisher's exact test. Analysis will be grouped by HCV subtype and DAA target (NS3/4A or NS5A). The analysis will include total number of subjects within each subtype with any variant within NS3, any variant within NS5A, and with variants in NS3 + NS5A.

The following will be included in the analyses of impact of baseline variants on treatment outcome:

- Variants at signature amino acid positions (vs no variant at that position), using detection thresholds of both 2% and 15%. The analysis will include the number of subjects with variants in NS3 only, in NS5A only, any in NS3, any in NS5A, any in NS5A, any in NS5A, any in NS5A.
- Variants at each non-signature amino acid position at a detection threshold of 15%.
- Each variant at signature amino acid position (vs not that variant) using detection thresholds of 2% and 15%. The analysis will include the number of subjects with variants in NS3 only, in NS5A only, any in NS3, any in NS5A, any in NS3 or NS5A, any in NS3 + NS5A.

Analysis 3: In subjects with or without polymorphisms in NS3 only, in NS5A only, any in NS3, any in NS5A, any in NS3 or NS5A, any in NS3 + NS5A at the *key subset of amino acid positions* at 15% detection threshold, the SVR_{12} rate will be calculated, and the rates with or without polymorphisms will be compared using Fisher's exact test.

Analysis will be separated by HCV subtype. The following tables will be provided (mITT-GT-VF):

- Comparison of SVR₁₂ rates by subtype, and total (include all subtypes)
- Comparison of SVR₁₂ rates by genotype, and total (include all subtypes)

Analysis 4 (will be available in the primary CSR and will updated in the final CSR for the study):

The following analyses will be performed for subjects who do not achieve SVR₁₂ (with separate summaries for subjects in PVF and non-PVF populations) and have post-baseline resistance data available:

- Listings by subject of all *treatment-emergent variants* relative to the baseline amino acid sequences will be provided for each DAA target (NS3/4A and NS5A).
- Listings by subject of all *variants at signature amino acid positions* in a postbaseline time point for each DAA target (NS3/4A and NS5A).
- The persistence of post-baseline variants at signature resistance-associated amino acid positions for each target (NS3 and NS5A) from subjects will be assessed at Post-Treatment Week 24. Listings by subject and time point of all treatment-emergent variants will be provided for each DAA target (NS3 and NS5A).

HCV Genotype/Subtype

Phylogenetic analysis will be conducted on HCV sequence from baseline samples from all subjects in order to accurately determine subtype.

Subjects' HCV genotype and subtype may be assessed based on the Inno-LiPA 2.0 Assay used by the Central lab (Covance), the HCV genotype determination by Sanger sequencing a region of NS5B by the Central lab (Covance) and/or from phylogenetic analysis of the full length NS3/4A, and/or NS5A sequences performed by AbbVie. If the

phylogenetic analysis is available, then it will be used to determine the subject's HCV genotype and subtype. If it is not available, then the Sanger sequencing assay result will be used to determine the subject's HCV genotype and subtype, if available. Finally, if neither the phylogenetic analysis result nor the Sanger sequencing assay results is available, then the Inno-LIPA assay results will be used to categorize the subject. This subtype information will be presented in summaries of efficacy subgroup analyses. The baseline characteristic summary will use the results from the central laboratory (Sanger sequencing or Inno-LiPA 2.0 Assay [if Sanger sequencing not available]).

This subtype information will be presented in summaries of efficacy subgroup analyses. The baseline characteristic summary will use the results from the central laboratory (Sanger sequencing or Inno-LiPA 2.0 Assay [if Sanger sequencing not available]).

A summary of HCV subtype as provided by the central laboratory (Sanger sequencing or Inno-LiPA 2.0 Assay [if Sanger sequencing not available]) versus phylogenetic analysis also will be provided.

10.8.1 Presence of Baseline Resistance-Associated Variants

For the efficacy subgroup analyses defined in Section 10.6, any NS3/4A variant and any NS5A variant are defined as follows, where baseline resistance-associated variants based on \geq 15% NGS detection threshold are considered. Signature amino acid positions of NS3/4A and NS5A by HCV genotype are listed in Table 7.

Signature Amino Acid Positions (All Variants at These				
Target	Genotype	Positions Are to Be Included)	Other Specific Variants	
NS3/4A	1, 2, 3, 4, 5, 6	155, 156, 168		
NS5A	1a	28, 30, 31, 93	H58D, E62A	
	1b	31, 93		
	2	24, 28, 30, 92, and 93		
	3	24, 28, 30, 31, 58, and 93		
	4	24, 28, 30, 31, and 93		
	5	24, 28, 30, 31, 58, 92, and 93		
	6	24, 28, 30, 31, 58, 92, and 93		

Table 7. Resistance-Associated Variants by DAA Target and HCV Genotype

For example, according to Table 7, all subjects with any baseline variant at amino acid positions 155, 156, or 168 will be counted as having any NS3/4A variant at baseline; any HCV genotype 2 subjects with any baseline variant at amino acid positions 24, 28, 30, 92, or 93 will be counted as having any NS5A variant at baseline.

The number and percent of subjects in the mITT-GT-VF population will be summarized for the presence of baseline resistance-associated variants of:

- 1. Any NS3/4A variant at baseline (yes/no);
- 2. Any NS5A variant at baseline (yes/no);
- 3. Any NS3/4A variant at baseline **or** any NS5A variant at baseline (yes/no);
- 4. Both NS3/4A and NS5A variant at baseline (i.e., any NS3/4A variant at baseline **and** any NS5A variant at baseline) (yes/no);
- 5. Presence or absence of any variant
 - 5a. Any NS3/4A variant at baseline only (i.e., without baseline NS5A variants);
 - 5b. Any NS5A variant at baseline only (i.e., without baseline NS3/4A variants);
 - 5c. Both NS3/4A and NS4A variant at baseline;

5d. None (i.e., no baseline variant in either NS3/4A or in NS5A at baseline).

10.9 Patient Reported Outcomes

The following instruments will be used to collect patient reported outcomes (PROs): SF-36 version 2 (SF-36v2), Fatigue Severity Scale (FSS), and EuroQol-5 Dimensions-3 Level (EQ-5D-3L).

Subject's responses to the EQ-5D-3L will be combined into a unique health state using a 5-digit code with 1 digit from each of the 5 dimensions. The EQ-5D-3L states will be converted into a single preference-weighted health utility index score by applying weights.^{1,2} The VAS score will be analyzed separately.

The SF-36v2 measures dimensions of a patient's functional health and well-being in 8 domains and also provides 2 summary scores that characterize a patient's mental (Mental Component Summary; MCS) and physical (Physical Component Summary; PCS) health status. Imputation will be applied to each domain as described in Section 6.3. The score for each of the 8 domains ranges from 0 to 100 and will be normalized according to the user manual.³ The standardization of the normalized scores will provide the norm-based scores with a mean of 50 and a SD of 10. The two summary scores are based on the norm-based scores. Per the SF-36v2 instrument manual, score for any item with multiple responses will be set to "missing." Subject's responses to the SF-36v2 will be summarized for the PCS and MCS measures and eight individual domain measures.

The FSS measures the impact of fatigue over the past week on specific types of functioning. The survey consists of 9 questions using a 7-point Likert scale. A total score is calculated as the average of the individual item responses (adding up all the answers and dividing by nine). Higher FSS scores indicate a higher degree of impact of fatigue. Imputation will be applied to the total score as described in Section 6.3.

Summary statistics (n and mean) at each visit and for change from baseline (n, mean, SD, minimum and maximum) to each visit will be provided for the SF-36v2 (MCS and PCS)

scores; FSS total score; and EQ-5D-3L health index score and VAS score and will be summarized descriptively at each visit and for change from baseline to each visit.

The following analyses of patient reported outcomes (PROs) also will be performed:

- Number and percentage of subjects who have ever experienced an increase from baseline up through each applicable time point of greater than or equal to 2.5 points in the SF-36 MCS and PCS, along with two-sided 95% Normal CI;
- Number and percentage of subjects who have ever experienced an increase from baseline up through each applicable time point of greater than or equal to 5 points in the SF-36 domain scores, along with two-sided 95% Normal CI;
- Number and percentage of subjects who have ever experienced an increase from baseline up through each applicable time point of greater than or equal to 0.7 in the FSS total score, along with two-sided 95% Normal CI.

If a subject starts another treatment for HCV, then all PRO values for this subject measured on or after the start date of the new HCV treatment will be excluded from analyses.

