- The percentage of subjects with post-treatment relapse.

The number and percentage of subjects meeting each secondary efficacy endpoint will be summarized along with 95% Wilson score confidence intervals.

Additional efficacy endpoints include: percentage of subjects with HCV RNA < LLOQ at each post-baseline visit during treatment period, percentage of DAA naïve subjects with on-treatment virologic failure and relapse, SVR₄, SVR₂₄, and the percentage of subjects who relapsed after achieving SVR₁₂; the number and percentage of subjects meeting each additional efficacy endpoint will be summarized along with 95% Wilson score confidence intervals.

Statistical Methods (Continued):

Pharmacokinetic:

Plasma concentration of ABT-493, ABT-530, and their possible metabolites will be tabulated for each subject. Summary statistics will be computed for each time and visit. Population pharmacokinetic analyses will be performed using the actual sampling time relative to dosing. Pharmacokinetic models will be built using a non-linear mixed-effect modeling approach. Individual blood concentrations of immunosuppressants, cyclosporine, sirolimus, everolimus, and/or tacrolimus, will also be tabulated and summarized.

PROs:

Change from baseline in the patient reported outcome summary measures will be summarized descriptively. In addition, the proportion of patients achieving a minimal important difference will be identified.

[figure not shown]
Resistance:

For all subjects receiving study drug, the HCV variants at signature resistance-associated amino acid positions at baseline identified by population or deep sequencing and comparison to the appropriate prototypic reference sequence will be analyzed.

The following resistance information will be analyzed for subjects receiving study drugs who do not achieve SVR_{12} and who have a post-baseline sample with HCV RNA \geq 1000 IU/mL: 1) the amino acid variants in available post-baseline samples identified by population or deep sequencing and comparison to the baseline sequences, 2) the amino acid variants in available post baseline samples at signature resistance-associated positions identified by population or deep sequencing, and comparison to the appropriate prototypic reference sequence, and 3) the persistence of post-baseline viral resistance by population or deep sequencing.

Safety:

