PRO instruments should be consistently presented as listed in Appendix C and Appendix D, so that subjects complete the questionnaires in the following order: the SF-36v2, FSS and EQ-5D-3L. The PRO instruments should be completed prior to study

drug administration on Day 1 and prior to any discussion of adverse events or any review of laboratory findings, including HCV RNA levels.

Short Form 36 (SF-36) – Version 2 Health Survey

The SF-36v2 is a general Health Related Quality of Life (HRQoL) instrument with extensive use across a broad variety of health conditions and is the standard in literature for HCV. The SF-36v2 instrument comprises 36 total items (questions) targeting a subject's functional health and well-being in 8 domains (physical functioning, role physical, bodily pain, general health, vitality, social functioning, role emotional and mental health). Domain scores are also aggregated into a Physical Component Summary score and a Mental Component Summary score. Higher SF-36v2 scores indicate a better state of health. The SF-36v2 should require approximately 10 minutes to complete.

Fatigue Severity Scale (FSS)

The FSS measures the impact of fatigue over the past week on specific types of functioning (e.g., motivation, exercise, physical functioning, carrying out duties, interfering with work, family, or social life). The survey consists of 9 questions using a 7 point Likert scale. A total score is calculated as the average of the individual item responses. The scale's psychometric properties have been confirmed in chronic hepatitis C and other diseases. The FSS should require approximately 5 minutes to complete.

EuroQol-5 Dimensions-3 Level (EQ-5D-3L)

The EQ-5D-3L is a health state utility instrument that evaluates preference for health status (utility). The 5 items in the EQ-5D-3L comprise 5 dimensions (mobility, self-care, usual activities, pain/discomfort, and anxiety/depression) each of which are rated on 3 levels of severity (no problems, some problems, unable to do/extreme problems). Responses to the 5 items encode a discrete health state which is mapped to a preference (utility) specific for different societies. Subjects also rate their perception

of their overall health on a separate visual analogue scale (VAS). The EQ-5D-3L should require approximately 5 minutes to complete.

Enrollment and Assignment of Subject Numbers

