8.1.3 Patient Reported Outcomes

The handling of missing data for patient reported outcomes (PROs) will be as follows. If a respondent answers at least 50% of the items in a multi-item scale of the SF-36v2, the missing items will be imputed with the average score of the answered items in the same scale. In cases where the respondent did not answer at least 50% of the items, the score for that domain will be considered missing. The missing items of the FSS questionnaire will be imputed with the average score of the answered items as long as more than 50% of the items on the FSS are answered. For EQ-5D-3L index and VAS scores, no imputation will be performed for missing items.

The mean change from baseline to each applicable post-baseline time point in the SF-36v2 Mental Component Summary (MCS) and Physical Component Summary (PCS) scores; FSS total score; EQ-5D-3L health index score and VAS score will be summarized descriptively at each visit and for change from baseline to each visit.

The following analyses of PROs will be performed:

• Cumulative number and percentage of subjects who have ever experienced an increase from baseline up through each applicable time point of greater than or equal to 2.5 points in the SF-36 MCS and PCS;

- Cumulative number and percentage of subjects who have ever experienced an increase from baseline up through each applicable time point of greater than or equal to 5 points in the SF-36 domain scores;
- Cumulative number and percentage of subjects who have ever experienced an increase from baseline up through each applicable time point of greater than or equal to 0.7 in the FSS total score.

[figure not shown]
Additional analyses of PROs may be performed as useful and appropriate.

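### The Fatigue Severity Scale responder count runs in the wrong direction: it counts subjects whose fatigue worsens by 0.7 or more

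*SAP*

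**What the plan says.** SAP 10.9 (Patient Reported Outcomes) describes the FSS this way: "The survey consists of 9 questions using a 7-point Likert scale". The total is the plain average of the item responses, and the section gives its direction: "Higher FSS scores indicate a higher degree of impact of fatigue".

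The section then lists three threshold analyses, each giving the number and percentage of subjects who ever crossed a threshold up to each time point. Two concern the SF-36v2: a rise of at least 2.5 points in the component summaries and of at least 5 points in the domain scores. The third concerns the FSS and counts "an increase from baseline up through each applicable time point of greater than or equal to 0.7 in the FSS total score"; the rule ends "greater than or equal to 0.7 in the FSS total score, along with two-sided 95% Normal CI", so a 95% normal-approximation interval goes with it.

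Protocol 8.1.3 has the same three analyses, and its FSS rule is again an "increase from baseline up through each applicable time point of greater than or equal to 0.7 in the FSS total score". The purpose is given in the protocol synopsis, under Statistical Methods: "the proportion of patients achieving a minimal important difference will be identified".

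On the SF-36v2, Protocol 5.3.1.1 says: "Higher SF-36v2 scores indicate a better state of health".

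**The concern.** The three rules share one template, a rise from baseline. That template suits the SF-36v2, where up is better. It does not suit the FSS, where up is worse. Applied as written, the FSS percentage is a deterioration rate listed beside two improvement rates, with nothing to tell the reader that its meaning has changed.

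Read with the synopsis, the percentage would be taken as the share of subjects who gained a meaningful benefit in fatigue. A real reduction in fatigue would then show as a low rate, and a real worsening as a high one. A programmer who followed the SAP faithfully would produce this table.

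**Working it through.** **No plan figure to reproduce.** Neither document gives an expected FSS change, a standard deviation or a responder proportion. The check is a comparison of texts, followed by an illustration on assumed values.

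**Comparison of texts**

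| Instrument | Better direction | Source | Change counted | What is counted |
|---|---|---|---|---|
| SF-36v2 component summaries | Up | Protocol 5.3.1.1 | Rise of at least 2.5 | Improvement |
| SF-36v2 domains | Up | Protocol 5.3.1.1 | Rise of at least 5 | Improvement |
| FSS total | Down | SAP 10.9 | Rise of at least 0.7 | Worsening |

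Three things could have rescued the FSS rule, and none is present:

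1. Reverse scoring. The total is the unreversed average of the items (Protocol 5.3.1.1, SAP 10.9).
2. A label marking the count as worsening. There is none.
3. A parallel count of decreases. None is planned.

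The list of changes in SAP 12.1 covers only resistance and subgroup analyses, so it does not explain the rule either.

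**Who is counted.** A subject whose only change is a fall of 0.7 or more is never counted. A subject who rises by 0.7 at any one visit is counted, even if fatigue later improves. If items are coded 1 to 7 (an assumption; the documents say only that the scale has 7 points), a subject with baseline above 7 - 0.7 = 6.3, the most fatigued group, can never be counted. Under a decrease rule the subjects excluded in this way are those below 1 + 0.7 = 1.7, who have little fatigue to lose.

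**Visits affected.** According to the notes to SAP Tables 1 and 3, PROs are collected at Day 1, end of treatment, Post-Treatment Week 12 and Post-Treatment Week 24 (or post-treatment discontinuation). All three post-baseline assessments are affected.

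**Illustration at one visit.** Assume that the change in FSS is normal with mean m and SD s, where negative means less fatigue.

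- Written rule: P(change ≥ 0.7) = 1 - Φ((0.7 - m)/s)
- Decrease rule: P(change ≤ -0.7) = Φ((-0.7 - m)/s)

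For m = -0.5 and s = 1.0 these are 1 - Φ(1.2) = 11.5% and Φ(-0.2) = 42.1%, or about 10 and 38 of 90 subjects.

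| Mean m | SD s | Written rule | Decrease rule |
|---|---|---|---|
| 0 | 1.0 | 24.2% | 24.2% |
| 0 | 1.5 | 32.0% | 32.0% |
| -0.5 | 1.0 | 11.5% | 42.1% |
| -0.5 | 1.5 | 21.2% | 44.7% |
| -1.0 | 1.0 | 4.5% | 61.8% |
| -1.0 | 1.5 | 12.9% | 57.9% |

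**Illustration of the ever rule.** With three post-baseline visits, m = -0.5, s = 1.0 and an assumed between-visit correlation of 0.5 to 0.7, simulation gives about 25% to 21% under the written rule and about 67% to 61% under the decrease rule.

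In both illustrations, the more fatigue improves, the lower the reported rate.

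**The case against.** The best defence is that the count of worsening is deliberate. Fatigue was among the most frequent adverse events in the Phase 2 studies (Protocol 3.0 and 5.6.4), so tracking a meaningful rise in FSS would not be absurd. The phrase about a minimal important difference stands only in the synopsis, which names no direction; SAP 10.9 and Protocol 8.1.3 do not use it. That the wording was carried over from the SF-36v2 is an inference.

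This cannot be strictly excluded, but no text supports it. Two of the three post-baseline assessments fall after dosing has ended, which fits poorly with a tolerability purpose, and fatigue as an adverse event is already covered by the safety tables. To speak of achieving a difference describes benefit. Even if worsening was meant, the plan would hold an unlabelled worsening rate beside two improvement rates and no count of improvement, so it would still need correcting.

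Three limits do stand:

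- The worsening rate is the opposite tail, not the complement of the improvement rate. Under the ever rule one subject can meet both at different visits.
- The analysis is descriptive, and PROs are not among the stated objectives. The FSS mean changes planned in SAP 10.9 keep their correct sign and would show a real fall in fatigue.
- A protocol edit means an amendment with ethics review, so the cost is more than one word if the protocol is changed for this alone.

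**Conclusion.** The concern holds. By the SAP's own statement of scale direction, the FSS rule counts deterioration, and no analysis in either document counts improvement of 0.7 or more. One of the three planned PRO threshold analyses therefore reports the wrong tail at every post-baseline assessment.

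The numerical effect depends on the true change in FSS, which the documents do not give. Over assumed mean changes from 0 to -1.0 and SDs of 1.0 to 1.5, the gap at a single visit runs from nil to about 57 percentage points (61.8% - 4.5% = 57.3). The direction of the error does not depend on these assumptions. The reading of the percentage as a benefit rate rests on taking the synopsis together with SAP 10.9.

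The primary endpoint, the sample size and the FSS mean-change summaries are untouched. The point is worth correcting before the analysis, but it does not threaten the trial's main conclusion.

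**What to change.** In SAP 10.9, define FSS response as a decrease from baseline of at least 0.7 in the total score, at any assessment up to each time point. If the count of increases is still wanted, keep it as a separate table whose title says worsening. State the direction of benefit for each instrument in the table titles or footnotes.

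Record the departure from the protocol in SAP 12.1. Protocol 8.1.3 already allows further PRO analyses, so the SAP can make the change now; the protocol wording can be aligned at the next amendment made for other reasons.

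The cost is one word in the SAP, one sign in the program and, if increases are kept, one extra labelled table. No new data are needed.
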